7.2 Study Conduct

Relevant protocol deviations will be identified for all subjects who are randomized. Relevant Protocol Deviation Criteria expected to affect the primary safety endpoint are as follows:

- Subject randomized but not dosed
- Error in treatment assignment resulting in a subject being dosed with an incorrect treatment. This deviation will include only subjects who received apixaban (any dose) but were assigned by the IVRS to receive VKA or subjects who received VKA but were assigned by the IVRS to receive apixaban (either dose).

7.3 Study Population

All summary tables will be presented by Apixaban /VKA, aspirin/placebo separately if applicable, and combination of treatment groups (apixaban/aspirin, apixaban/aspirin placebo, VKA /aspirin, VKA /aspirin placebo).

The number of subjects enrolled into the study, and the number of subjects enrolled but not randomized together with the reasons for not being randomized will be summarized. The reasons for not being randomized will be taken from the CRF pre-randomization status page.

The summaries described below will also be presented by indication at enrollment (PCI/ACS).

The number of randomized subjects and the number of subjects discontinuing during intended treatment period together with the reasons for discontinuation will be summarized by treatment group. The reasons for discontinuation will be taken from the end-of-treatment visit page of CRF. The frequency of subjects enrolled in each country and in each site will be tabulated by randomized treatment group and for all randomized subjects combined.

The summary of VKA categories by warfarin and non-warfarin will be presented as well. The non-warfarin VKAs will be broken down by subcategories.

7.3.1.1 Demography and Baseline Characteristics

Demographic and baseline characteristics will be summarized by randomized treatment group, using the Randomized Population for oral anticoagulant and Randomized Population for antiplatelet. All summaries will be further tabulated by indication at enrollment (PCI/ACS). Continuous variables will be summarized using means, standard deviations, minima, maxima and quartiles, and categorical variables will be summarized using absolute and relative frequencies.

The following demographic and baseline characteristics will be summarized

- Indication at enrollment (where applicable)

- Apixaban dose at randomization
- Geographic region
- Age
- Age group (< 65, 65-<80, ≥80 years)
- Gender
- Race
- Ethnicity (for US only)
- Weight
- Weight group (≤ 60, > 60 kg)
- Serum Creatinine
- CHADS2 Score
- CHADSVASC2 score
- HASBLED score
- Hypertension
- Heart failure
- Diabetes Mellitus
- P2Y12 Concomitant medication
- Prior warfarin/ VKA status
- Prior use of Antiplatelet (where applicable)
- Prior Oral anticoagulant (where applicable)

7.4 Extent of Exposure

7.4.1 Study Therapy

The summaries described below will be tabulated for the Treated Populations. All summaries will be tabulated by treatment group and by indication at enrollment (PCI/ACS).

Length of exposure to study drug is defined as the number of days the subject is known to be on study drug. The distribution of the length of exposure to study drug will be presented by treatment group; this distribution will be presented by taking into account days without dosing. The distribution categories will be <30 days, 30 to <60 days, 60 to <90 days, 90 to <120 days, 120 to <150 days, 150 to <180 days, ≥ 180 days.

The length of exposure to study drug will also be summarized by treatment group using means, standard deviations, medians, minima and maxima. The total patient-days of exposure to study drug (say, T) will be presented for each treatment group and is defined as:

$$\sum_{i=1}^{N_T} \text{Length of exposure(days) for subject } i ,$$

where N_T represents the number of subjects receiving treatment T .

Treatment compliance (TC) will be summarized for apixaban and aspirin/placebo. The TC will be calculated using the following formula (assuming that either on the first day or the last day subjects only receives one dose of apixaban):

$$TC = \frac{\text{number of tablets taken}}{(\text{Number of days from first to last dose of study drug} - 1) \times n + 1} \cdot 100\%$$

Where n=1 for aspirin/placebo (QD), and n=2 for apixaban.

The frequency of subjects with at least 80% compliance with apixaban and aspirin/placebo will also be summarized.

7.4.2 INR Control

The summaries described below will be tabulated for the Randomized Population for oral anticoagulant.

For subjects who receive VKA, INR control is a more appropriate measure of compliance than pill count. The assessment of INR control will be based on all available INR values.

INR values will be summarized by visit (see [Sections 8.3](#)). These summaries will also be graphically displayed using a box plot.

The proportion of time (counted from first INR value recorded on or after dosing on Day 10 until the day of discontinuation of study drug without considering interruptions) in which subjects have an INR in the following ranges will be summarized:

- INR < 2.0, 2.0 ≤ INR ≤ 3.0, INR > 3.0

The frequency of subjects with INR in the 2.0-3.0 range for ≥ 60%, ≥ 65%, ≥ 70%, ≥ 75%, or ≥ 80% of time will also be summarized.

Only subjects who have received study drug for at least 10 days will be included in these time-related summaries.

The INR control measure, proportion of time in each INR interval, is calculated using Rosendaal's method which assumes that the INR value between two measurements varies linearly from the first value to the second value.

- let INR_i and INR_{i+1} be the two consecutive INR values
- let D_i and D_{i+1} be the dates associated with these two consecutive INR values, $[(D_{i+1} - D_i) = k, k > 1]$
- assuming the linear increase or decrease between the two consecutive INR measurements, the unit change per day in INR is $m = (INR_{i+1} - INR_i) / (D_{i+1} - D_i)$
- the estimated INR value for the date after D_i ($D_i + 1$) will be $INR_i + (m * 1)$
- likewise, the estimated INR value for the date ($D_i + 2$) will be $INR_i + (m * 2)$, etc.; the estimated INR value on the date immediately prior to D_{i+1} will be $INR_i + (m * (k - 1))$.

Using Rosendaal's method¹, each subject will have an INR measurement every day, either actual or by estimation through linear interpolation. The proportion of time subjects have an INR within an interval is the number of days with INR in the interval divided by the total number of days.

7.4.3 Concomitant Medications

The summaries described below will be tabulated for the Treated Populations. All summaries will be tabulated by treatment group and by treatment group and indication at enrollment (PCI/ACS).

The frequency of subjects receiving P2Y12 concomitant medication will be summarized by treatment group and medication class.

The length of exposure to P2Y12 administered concomitantly with study drug will be summarized (using means, standard deviations, medians, minima and maxima) by treatment group. The summaries will be presented by drug name.

7.5 Efficacy

There is no primary efficacy analysis for this study. All analyses described in this section will be performed on the Randomized Populations during Intended Treatment Period, and events will be confirmed by adjudication. The numbers of efficacy events will be summarized by combination of treatment groups (apixaban/aspirin, apixaban/aspirin placebo, VKA /aspirin, VKA /aspirin placebo).

Censoring scheme for time to efficacy event analyses: subjects who do not experience an efficacy endpoint event will be censored at the earlier of the date of end of Intended Treatment Period, death date (when death is not part of the endpoint), or last-contact date (for subjects who withdraw consent to be followed up or are lost to follow-up) at the end of Intended Treatment Period.

7.5.1 The comparison between apixaban and VKA

7.5.1.1 Secondary Efficacy Endpoints

The secondary efficacy endpoints are time to first occurrence of composite of all-cause death (will use “death” in later sections) and all-cause re-hospitalization and composite death and ischemic events (stroke, myocardial infarction, stent thrombosis, urgent coronary revascularization).

A Cox proportional hazards model including treatment group as a covariate and stratified by indication at enrollment (PCI/ACS) and antiplatelet (aspirin/placebo) will be used for randomized subjects for oral anticoagulant during Intended Treatment Period. A point estimate and two-sided 95% CI for hazard ratio will be calculated. A p-value for the test of equality (HR = 1) will be calculated based on the hierarchical testing strategy.

7.5.2 The comparison between aspirin and placebo

7.5.2.1 Secondary Efficacy Endpoint

The secondary efficacy endpoints are time to first occurrence of all-cause death and all-cause re-hospitalization and composite death and ischemic events (stroke, myocardial infarction, stent thrombosis, urgent coronary revascularization).

A Cox proportional hazards model including treatment group as a covariate and stratified by indication at enrollment (PCI/ACS) and anticoagulant treatment group (apixaban/VKA) will be used for randomized subjects for antiplatelet during Intended Treatment Period. A point estimate and two-sided 95% CI for hazard ratio will be calculated. A p-value for the test of equality (HR = 1) will be calculated based on the hierarchical testing strategy, similar to the analyses for apixaban vs. VKA.

7.6 Safety

All analyses described in this section will be performed on the Treated Populations during treatment period, and bleeding events will be confirmed by adjudication. The numbers of safety events will be summarized by combination of treatment groups (apixaban/aspirin, apixaban/aspirin placebo, VKA /aspirin, VKA /aspirin placebo).

Censoring scheme for time to event analyses of safety endpoints: subjects who do not experience a safety endpoint event will be censored at the earlier of 2 days after discontinuation of study drug, death date, or last-contact date (for subjects who withdraw consent to be followed up or are lost to follow-up) at the end of the treatment period.

7.6.1 The comparison between apixaban and VKA

7.6.1.1 Analysis of Primary Safety Endpoints

NI and Superiority Tests

All analyses described in this section will be performed on the treated subjects for oral anticoagulant during the treatment period using safety censoring scheme (considering study drugs apixaban/VKA).

The primary objective of the study is to determine if apixaban is NI to VKA for the primary safety endpoint (confirmed ISTH major bleeding and CRNM bleeding). Following the sequential testing strategy outlined in [Section 7.1](#), if non-inferiority for the primary safety endpoint is demonstrated at the one-sided 0.025 significance level then superiority of apixaban relative to VKA for the primary safety endpoint will be tested at the one-sided 0.025 significance level.

The analysis of primary safety endpoint will be performed using a Cox proportional hazard model including oral anticoagulant treatment group (apixaban/VKA) as a covariate and stratified by indication at enrollment (PCI/ACS) and antiplatelet (aspirin/placebo). The treatment effect will be

measured by the estimated HR and two-sided 95% CIs for HR. The non-inferiority will be demonstrated if the upper bound of two-sided 95% CIs for HR is less than 1.2.

The proportional hazards assumption will be checked by examining the plots of the log(-log(survival)) versus survival time for each stratum included in the Cox proportional hazards model.

Interaction between oral anticoagulant (apixaban/VKA) and antiplatelet (aspirin/placebo) is not anticipated, but this assumption will be examined within Cox model including stratification variable indication at enrollment (PCI/ACS), and terms of oral anticoagulant treatment group (apixaban/VKA), antiplatelet (aspirin/placebo), and oral anticoagulant (apixaban/VKA) by antiplatelet (aspirin/placebo) interaction. If quantitative interaction is significant (two sided p-value < 0.1), then qualitative interaction will be assessed using Gail and Simon test (1985)².

Event rates will be estimated and Kaplan-Meier curves will be plotted for the time from first dose of study medication to first occurrence of ISTH major or CRNM bleeding, by treatment group, by treatment group and indication at enrollment (PCI/ACS), and by treatment group and antiplatelet treatment group.

7.6.1.2 Sensitivity Analyses for Key Measures

To assess the impact of relevant protocol deviations on the NI assessment, the NI test will also be performed on the Evaluable Population during treatment period.

Sensitivity analysis of primary safety endpoint will be performed using randomized subjects for oral anticoagulant during treatment period as well.

7.6.1.3 Subgroup Analyses

All analyses described in this section will be performed on the Treated Population for oral anticoagulant during treatment period using the safety censoring scheme.

Table 7.6.1.3 shows the subgroups of interest for analyses of primary safety assessment. If the value of the grouping variable cannot be determined for a subject, the subject will be excluded from the corresponding subgroup analysis. For each subpopulation analysis, if, in any treatment group, the number of events is ≤ 10 for a subgroup, then the grouping variable will not be included in the test of treatment by subpopulation interaction.

Table 7.6.1.3: Subgroups of Interest for Primary Safety Assessments

Grouping Variable	Subgroups
indication at enrollment	PCI ACS
Apixaban dose*	2.5 mg BID 5 mg BID
Geographic region	North America Latin America Europe

Table 7.6.1.3: Subgroups of Interest for Primary Safety Assessments

Grouping Variable	Subgroups
	Asia/Pacific
Age	< 65 years old ≥65 to < 80 years old ≥ 80 years old
Gender	Male Female
Race	White Black / African American Asian Other
Ethnicity (for US only)	Hispanic/Latino Not Hispanic/Latino
Weight	≤ 60 kg > 60 kg
Serum Creatinine	< 1.5 mg/dL ≥1.5 mg/dL
CHADS2 Score	≤ 1 2 ≥ 3
CHADSVASC2 scores	Low (0[male] or 1 [female]) Moderate (1 [male]) High (≥ 2)
HASBLED score	≤ 1 2 ≥ 3
Diabetes Mellitus	Yes No
Hypertension requiring pharmacological treatment	Yes No
Heart Failure	Yes No
Concomitant med (which P2Y12 agent was the subject on)	Clopidogrel Prasugrel Ticlodipine Ticagrelor
Prior warfarin/VKA status at least 2 months prior to the study	Experienced Naive
Antiplatelet	Aspirin

Table 7.6.1.3: Subgroups of Interest for Primary Safety Assessments

Grouping Variable	Subgroups
	Aspirin placebo

*the control for apixaban 2.5 mg will be subjects in the VKA group who meet criteria of apixaban dose adjustment (see section 1); other VKA subjects will be the control for the subjects taking apixaban 5 mg.

Each of these subgroups will be analyzed using a Cox proportional hazards model stratified by indication at enrollment (not applicable for the first subgroup listed) and antiplatelet (aspirin/placebo) (not applicable for the last subgroup listed) with terms for treatment group. The estimated HR and two-sided 95% CIs will be calculated to assess the treatment effect within each of the subgroups. The p-value for the test of the treatment by grouping variable interaction will be presented based on a Cox proportional hazards model stratified by indication at enrollment (not applicable for the first subgroup listed) and antiplatelet (aspirin/placebo) (not applicable for the last subgroup listed with terms for treatment group,) with terms for treatment group, and the grouping variable and treatment by grouping variable interaction.

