#### 4.5 Selection and Timing of Dose for Each Subject

Subjects randomized to apixaban will be dosed at 5 mg bid, unless they meet at least two of the following criteria for dose reduction to 2.5 mg BID:

- Age  $\geq$  80 years
- Weight  $\leq$  60 kg
- Serum creatinine  $\geq$  1.5 mg/dL (133 micromol/L)

Subjects randomized to apixaban may have their dosages increased or decreased during the 6 month treatment period if at least two of the three above criteria change during the study.

Subjects randomized to VKA should be titrated up for an INR target goal of 2.0 to 3.0. Dosages of VKA to achieve that range should be per local standards of care and per investigator clinical judgment.

Both the oral anticoagulant (apixaban or VKA) and the antiplatelet agents (blinded aspirin once daily or blinded placebo once daily) must be started within 24 hours of randomization.

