## 5 STUDY ASSESSMENTS AND PROCEDURES

### 5.1 Flow Chart/Time and Events Schedule

**Table 5.1-1: Baseline and Randomization (CV185316)**

Procedure	Screening/ Randomization Visit	Notes
Eligibility Assessments		
Informed Consent	X	
Inclusion/Exclusion Criteria	X	
Medical History	X	Include assessment of alcohol use, tobacco use, prior VKA use, and CHADS-VASC and HAS-BLED scores
Safety Assessments		
Physical Examination	See Notes	Only if deemed necessary by treating physician. Results of examination will be documented in patient's chart, not on CRF
Vital Signs	X	Blood Pressure and Weight
Assessment of Signs and Symptoms	See Notes	Only if deemed necessary by treating physician. Results of assessment will be documented in patient's chart, not on CRF
Serious Adverse Events Assessment	See Notes	Refer to section 6.1 of the protocol for SAE definitions applying to this study.
Adverse Events Assessment	N/A	
Laboratory Tests	X	Local lab: CBC, chemistry(CHEM7 or equivalent for determination of serum creatinine), coagulation (for PT/PTT/INR) (local lab within 7 days can be used)
Urine Pregnancy Test* ( WOCBP only )	X	*If applicable Serum pregnancy test to be performed only if urine test is positive or un-interpretable
Study Drug		
Randomize	X	
Dispense Study Drug (administer within 24 hours of randomization)	X	Those supplied by BMS or sourced by the investigator

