7 STATISTICAL ANALYSES

7.1 General Methods

All analyses will be performed in SAS[®] using version 9.2 or higher. Unless otherwise stated, all hypothesis tests will be performed using two-sided tests at the 5% significance level.

Continuous variables will be summarized using descriptive statistics including means, standard deviations, minima, maxima and quartiles, and qualitative or discrete variables will be summarized using absolute and relative frequencies.

Time to Event Analyses

Unless specified, calculation of p-values and construction of point estimates and CIs for HR will be based on Cox proportional hazard models. Stratification variables will be included in the model as stratification factors. Additional covariates may be included as described in [Sections 7.5](#) and [7.6](#). Ties will be handled using Breslow's methodology.

Event rates will be estimated and plotted over time using Kaplan-Meier methodology.

Testing Strategy

A hierarchical testing strategy described below will be used to compare the effects of apixaban and VKA between treatment groups.

- Non-inferiority (NI) for the primary endpoint, a composite of ISTH major and CRNM bleeding, will be tested first.
- If NI is not demonstrated, then nominal p-values will be presented for subsequent comparisons between apixaban and VKA
- If NI is demonstrated, then superiority for the composite of ISTH major and CRNM bleeding will be tested. If superiority is not demonstrated, then nominal P-values will be presented for subsequent comparisons between apixaban and VKA.
- If superiority for the composite of ISTH major and CRNM bleeding is demonstrated, then superiority for the composite of all-cause death and all-cause re-hospitalization will be tested. If superiority is not demonstrated, then nominal p-values will be presented for subsequent comparisons between apixaban and VKA.

- If superiority for the composite of all-cause death and all-cause re-hospitalization is demonstrated, then the composite of all-cause death and ischemic events will be tested.

All tests will be performed at the two-sided $\alpha = 0.05$ significance level.

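### The apixaban-dose subgroup sorts apixaban subjects by dose but VKA controls by dose-adjustment criteria, so a dose row can compare unlike patients

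*SAP*

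**What the plan says.** SAP section 7.6.1.3 lists an apixaban-dose subgroup with rows for 2.5 mg BID and 5 mg BID. VKA subjects have no apixaban dose, so a footnote to Table 7.6.1.3 supplies their allocation: "the control for apixaban 2.5 mg will be subjects in the VKA group who meet criteria of apixaban dose adjustment", and "other VKA subjects will be the control for the subjects taking apixaban 5 mg". The footnote takes the criteria from SAP section 1, which is not in the text available for this review. Protocol section 4.5 is assumed to give the same ones: 5 mg for subjects randomized to apixaban, "unless they meet at least two of the following criteria for dose reduction to 2.5 mg BID". The three criteria are age 80 years or over, weight 60 kg or less, and serum creatinine 1.5 mg/dL or more. Section 4.5 also allows the dose to change during treatment.

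The footnote does not say which dose counts. SAP section 7.3.1.1 lists "Apixaban dose at randomization" among the baseline characteristics, and that reading is used here.

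On the model, the SAP says: "Each of these subgroups will be analyzed using a Cox proportional hazards model stratified by indication at enrollment", with antiplatelet assignment as the other stratum. An interaction p-value is presented for each grouping variable. Under SAP section 7.1, unless otherwise stated, "all hypothesis tests will be performed using two-sided tests at the 5% significance level".

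**The concern.** Criteria status is a baseline fact known in both arms. Dose is set after allocation and exists in one arm only. Using one to place apixaban subjects and the other to place VKA subjects means that randomization no longer guarantees like-with-like within a row. An apixaban subject whose dose does not match the criteria is set against VKA subjects of the opposite criteria status.

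If the criteria predict bleeding, non-qualifying subjects on 2.5 mg lower the average risk of the apixaban side of that row, while its VKA side contains only qualifying subjects. The row then favours apixaban even if apixaban and VKA do not differ. The 5 mg row moves slightly the other way, so an apparent dose interaction can arise from sorting alone.

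Nothing else in the plan repairs this:

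- The subgroup model has no age, weight or creatinine term.
- The treatment-error deviation in SAP section 7.2 covers only receipt of the other anticoagulant, so a 2.5 mg/5 mg mismatch is not a listed deviation.
- The subgroup analysis uses the Treated Population, so mismatched subjects stay in.
- The sensitivity analyses in SAP section 7.6.1.2 do not address the dose rows.

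**Working it through.** The documents give no figure for this subgroup, so there is none to reproduce. They also give no share meeting the criteria, no mismatch rate and no bleeding risk by criteria status. The calculation is an illustration on stated assumptions.

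**Inputs**

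- From the documents: 4600 subjects allocated 1:1, so n = 2300 per arm; planned VKA rate 9% per half year; two-sided 5% level for the interaction test.
- Assumed: share meeting the criteria m = 0.10; six-month risk r1 = 0.14 if met and r0 = 0.085 if not; no true treatment effect. Overall risk is 0.10 × 0.14 + 0.90 × 0.085 = 0.0905, close to the planned 9%.
- Varied: u, the share of qualifying subjects on 5 mg, and o, the share of non-qualifying subjects on 2.5 mg.

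**Formulas (apixaban/VKA risk ratio; true value 1.00)**

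- 2.5 mg row: {[m(1−u)r1 + (1−m)o·r0] / [m(1−u) + (1−m)o]} / r1
- 5 mg row: {[m·u·r1 + (1−m)(1−o)r0] / [m·u + (1−m)(1−o)]} / r0
- SE of a log ratio: √(1/events on apixaban + 1/events on VKA)
- Interaction z: difference of the two log ratios over the root of the summed squared SEs. The false-positive rate is the chance that a unit normal variable centred at z exceeds 1.96 in absolute value.

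**Worked case, u = 0.10 and o = 0.03**

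- 2.5 mg row: (0.09 × 0.14 + 0.027 × 0.085) / 0.117 = 0.1273, and 0.1273/0.14 = 0.909.
- Mismatched share of the apixaban side: 0.027/0.117 = 23.1%.
- Events: 2300 × 0.014895 = 34.3 on apixaban and 2300 × 0.10 × 0.14 = 32.2 on VKA. SE = √(1/34.3 + 1/32.2) = 0.245, and ln(0.909)/0.245 = −0.39.
- 5 mg row: (0.01 × 0.14 + 0.873 × 0.085) / 0.883 / 0.085 = 1.007.
- Interaction z = −0.38, so the false-positive rate is 6.7%.

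**All cases**

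| u, o | Mismatched share of 2.5 mg row | 2.5 mg ratio | 5 mg ratio | Shift of 2.5 mg row | Interaction false positives |
|---|---|---|---|---|---|
| 0, 0 | 0% | 1.000 | 1.000 | 0 | 5.0% |
| 0.05, 0.01 | 8.7% | 0.966 | 1.004 | 0.14 SE | 5.2% |
| 0.10, 0.03 | 23.1% | 0.909 | 1.007 | 0.39 SE | 6.7% |
| 0.20, 0.06 | 40.3% | 0.842 | 1.015 | 0.71 SE | 10.9% |

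A simulation with exponential event times and 10,000 trials per case agrees: 2.5 mg row ratios of about 0.96, 0.90 and 0.83, and interaction rejection of about 5%, 7% and 12%. With the same baseline rule in both arms, the ratio is about 1.00 and rejection about 5%.

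**What drives the shift**

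- One direction at a time: o = 0.03 alone gives 0.92 in the 2.5 mg row. u = 0.10 alone leaves that row at 1.00 and puts the 5 mg row at 1.007. Almost all of the shift comes from non-qualifying subjects on 2.5 mg.
- Risk gap, with u = 0.10, o = 0.03 and overall risk held at 9.05%: ratio 1.00 with no gap, 0.98 at 10% vs 8.9%, 0.94 at 12% vs 8.7%, and 0.91 at 14% vs 8.5%.

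**Second check on the hazard scale, true HR 0.90 throughout**

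Take 10% qualifying, a hazard twice as high in them, 5% of non-qualifying subjects on 2.5 mg and 20% of qualifying subjects on 5 mg. The 2.5 mg row HR is 0.90 × (0.08 × 2 + 0.045) / 0.125 / 2 = 0.74. The 5 mg row HR is 0.90 × (0.02 × 2 + 0.855) / 0.875 = 0.92. Over wider assumptions (5–20% qualifying, hazard 1.5–2.0 times higher, mismatches of 2–10% and 10–30% respectively), the 2.5 mg row runs from 0.88 down to 0.57 and the 5 mg row from 0.90 to 0.97. With both arms sorted by the criteria, every row returns 0.90.

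**The case against.** The strongest reply is that protocol section 4.5 ties the dose to the criteria. If it is followed, the two sorting rules coincide and the bias is zero. Nothing in the documents shows that it will not be followed, and every quantity that sets the size of the effect is assumed. This stands, and it is why the figures above are only an illustration.

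A second point concerns one input. The calculation gives mismatched subjects on 2.5 mg the average non-qualifying risk of 8.5%. They could instead be subjects just short of two criteria, with higher risk. At 11.5% for them, the middle case becomes (0.09 × 0.14 + 0.027 × 0.115) / 0.117 / 0.14 = 0.96 rather than 0.91, and at 14% it is 1.00. The arithmetic is right: the shift could be smaller than shown. It does not remove the mismatch in the definition.

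Third, the plan has partial safeguards. Age, weight and serum creatinine are separate subgroups, cut at the same values as the criteria and defined identically in both arms, but none gives the two-of-three combination. The interaction test is also dropped when any treatment group has 10 or fewer events in a subgroup. With 3% qualifying, 2300 × 0.03 × 0.14 = 9.7 events would be expected, so it would often be dropped. The row hazard ratios would still be reported.

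Finally, a criteria-based subgroup answers a different question from one based on dose received. That is so, but the footnote already uses criteria for half of the comparison, and no VKA subject has an apixaban dose to match on.

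**Conclusion.** The concern holds and is minor. The footnote uses different sorting rules in the two arms, and nothing in the available text corrects for it. Any bias needs three things: apixaban doses that do not match the criteria, criteria that predict bleeding, and mismatched subjects whose risk differs from that of the controls in their row. The documents establish none of these. Under the main illustrative assumptions the 2.5 mg row moves by 0.14 to 0.71 standard errors, and the interaction test's false-positive rate goes from 5% to between 5.2% and 10.9%. The wider hazard-scale assumptions give larger shifts.

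The effect is confined to two subgroup rows and one interaction p-value, to which the SAP attaches no decision rule. The primary non-inferiority test, the superiority test, the rest of the hierarchy and the sample size are unaffected. The conclusion assumes that SAP section 1 repeats the protocol criteria and that dose means dose at randomization. If a later dose were used, a further post-randomization element would enter. No view is taken on dosing itself.

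**What to change.** In SAP Table 7.6.1.3, define this subgroup in both arms by one baseline variable: whether the subject meets at least two of the three protocol section 4.5 criteria at randomization (yes/no), from baseline age, weight and serum creatinine. Report the apixaban dose descriptively, with the number of apixaban subjects whose dose at randomization does not match the criteria.

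As clean-up, use the same variable in Table 7.6.2.2 and delete the identical footnote there. That table compares aspirin with placebo, so a VKA control group has no meaning in it, although the bias described here does not arise there.

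The cost is SAP wording only. Age is already a baseline characteristic, and protocol Table 5.1-1 collects weight and laboratory tests in all subjects at randomization ("CHEM7 or equivalent for determination of serum creatinine"). The one loss is that the subgroup no longer describes dose received, which the descriptive table covers.
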